## 4.2.3. Elimination from Modified full analysis set (mFAS)

### 4.2.3.1. Excluded subjects

A subject will be excluded from the mFAS analysis if excluded from the FAS and under the following additional conditions:

Code	Condition under which the code is used	Visit (V) (timepoints) where the code is applicable	Applicable for endpoint [HUM=humoral response, CMI=CMI response]
1030.b	Not administering any NTHi-Mcat vaccine	All	HUM, CMI
1070.a	Incomplete treatment course	All	HUM, CMI
1070.a	Other deviations related to wrong treatment administered (including randomization failure)	All	HUM, CMI
2080	Subjects did not comply with Sh_NTHi-Mcat vaccination schedule	V3_1, V3_3, V3_6	HUM, CMI

Note: CMI elimination codes are applicable only to subjects belonging to the CMI sub-cohort.

**CONFIDENTIAL**

209538 (NTHI MCAT-009)  
 Statistical Analysis Plan Amendment 2

**4.2.4. Elimination from Per-protocol analysis set (PPS)****4.2.4.1. Excluded subjects**

A subject will be excluded from the PPS analysis if excluded from the mFAS and under the following additional conditions:

Code	Condition under which the code is used	Visit (V) (timepoints) where the code is applicable	Applicable for endpoint [HUM=humoral response, CMI=CMI response]
1040	Administration of concomitant vaccine(s) forbidden in the protocol	All	HUM, CMI
1070	Vaccination not according to protocol	All	HUM, CMI
1080	Vaccine temperature deviation	All	HUM, CMI
1090	Expired vaccine administered	All	HUM, CMI
2010	Protocol violation (inclusion/exclusion criteria)	All	HUM, CMI
2040	Administration of any medication forbidden by the protocol	All	HUM, CMI
2050	Medical condition forbidden by the protocol	All	HUM, CMI
2080	Subjects did not comply with vaccination schedule	All	HUM, CMI
2090.a	Subjects did not comply with blood sample schedule (sample for humoral immune response)	All	HUM
2090.b	Subjects did not comply with blood sample schedule (sample for CMI response)	All	CMI
2100.a	Humoral immune response results not available	All	HUM
2100.b	CMI response results not available	All	CMI
2120.a	Obvious incoherence or abnormality or error in data (data on humoral immune response)	All	HUM
2120.b	Obvious incoherence or abnormality or error in data (data on CMI response)	All	CMI

Note: CMI elimination codes are applicable only to subjects belonging to the CMI sub-cohort. In case of missed assessment or assessment not properly performed, the codes 2100c and 2120c can be applicable; decision is taken case by case.

**4.2.5. Elimination from unsolicited and solicited safety set****4.2.5.1. Excluded subjects****4.2.5.1.1. Unsolicited safety set**

Code 1030.b (not administering any NTHi-Mcat vaccine), code 800 (fraudulent data) and code 900 (invalid informed consent) and code 1150 (no post-vaccination safety data) will be used to identify subjects eliminated from the unsolicited safety set.

**CONFIDENTIAL**

209538 (NTHI MCAT-009)  
 Statistical Analysis Plan Amendment 2

Code 1150 will be attributed to subjects if all the following conditions are met: subject did not complete the safety assessment following the 7-day follow-up period after NTHi-Mcat vaccinations (i.e. phone contacts), did not return the pDiary, did not return for the scheduled visit 30-days after the NTHi-Mcat vaccinations and did not report any unsolicited AE.

Code 1070.a will be used to identify subjects eliminated from the Unsolicited Safety Set by visit when the NTHi-Mcat vaccination is not administered at that visit.

#### **4.2.5.1.2. *Solicited safety set***

Code 1030.b (not administering any NTHi-Mcat vaccine), code 800 (fraudulent data) and code 900 (invalid informed consent) and code 1160 (no post-vaccination solicited safety data) will be used to identify subjects eliminated from the solicited safety set.

Code 1070.a will be used to identify subjects eliminated from the Solicited Safety Set by visit when the NTHi-Mcat vaccination is not administered at that visit.

## **5. STATISTICAL ANALYSES**

Note that standard data derivation rules and statistical methods are described in “business rules document” and will not be repeated below. The study specific data derivation rules and statistical methods will be described in Section 9.

### **5.1. Demography**

#### **5.1.1. Analysis of demographics/baseline characteristics planned in the protocol**

Demographic characteristics (including age at first study vaccination in years, gender, race, ethnicity and smoking status) will be summarized by study group and overall, using descriptive statistics:

- Frequency tables will be generated for categorical variables such as smoking status.
- Mean, standard deviation, median, minimum and maximum will be provided for continuous data such as age, height and weight.

Withdrawal status will be summarized by group using descriptive statistics:

- The numbers of withdrawn subjects will be tabulated according to the reason for withdrawal
- The number of subjects enrolled into the study as well as the number of subjects excluded from the PPS and mFAS will be tabulated.

**CONFIDENTIAL**209538 (NTHI MCAT-009)  
Statistical Analysis Plan Amendment 2**5.1.2. Additional considerations**

Summaries of demographic/baseline characteristics will include: age, country, centre, gender, race, ethnicity, smoking status, pack-years and vital signs (including body mass index [BMI]).

**5.2. Exposure****5.2.1. Analysis of exposure planned in the protocol**

None.

**5.2.2. Additional considerations**

The number and percentage of subjects who received study vaccine doses will be tabulated for each study group (based on the ES).

**5.3. Immunogenicity****5.3.1. Analysis of immunogenicity planned in the protocol**

The primary analysis will be based on the PPS. A supplementary analysis may be based on the mFAS.

Endpoint	Statistical analysis methods
Primary	
Between group assessment
 
Considering the sampling timepoint at 1 month after Dose 2 of NTHi-Mcat vaccine, the 2-sided 95% CIs for the group GMC ratio (Sh_NTHi-Mcat_1; _3; _6 group over NTHi-Mcat group) of anti-PD, anti-PE, anti-PiLA, anti-UspA2 will be computed using an analysis of covariance (ANCOVA) model on the logarithm10 transformation of the concentrations. The ANCOVA model will include study group, smoking status (current or former), age category (50–59, 60–69, 70–80 years of age) and centre as factors and the antibody concentration before Dose 1 as covariate.
 
Non-inferiority for a specific time-lag will be claimed if the lower limit of the 2-sided 95% CI for the GMC ratio will be above 0.667 for all anti-PD, anti-PE, anti-PiLA, anti-UspA2. The sequential procedure for multiple time-lags will be used: starting from the 6-months lag, the 3-months NI will be tested only if the 6-months NI will be demonstrated, while the 1-month NI will be tested only if the 6-months and 3-months NI will be both demonstrated.

**CONFIDENTIAL**209538 (NTHI MCAT-009)  
Statistical Analysis Plan Amendment 2

Endpoint	Statistical analysis methods
The following modification of the primary objective will be applicable if the per-protocol set is not reached for the Sh_NTHi-Mcat_6 group:	
Considering the sampling timepoint at 1 month after Dose 2 of NTHi-Mcat vaccine, the 2-sided 95% CIs for the group GMC ratio (Sh_NTHi-Mcat_1; _3 group over NTHi-Mcat group) of anti-PD, anti-PE, anti-PiA, anti-UspA2 will be computed using an analysis of covariance (ANCOVA) model on the logarithm10 transformation of the concentrations. The ANCOVA model will include study group, smoking status (current or former), age category (50–59, 60–69, 70–80 years of age) and centre as factors and the antibody concentration before Dose 1 as covariate.
 
Non-inferiority for a specific time-lag will be claimed if the lower limit of the 2-sided 95% CI for the GMC ratio will be above 0.667 for all anti-PD, anti-PE, anti-PiA, anti-UspA2. The sequential procedure for multiple time-lags will be used: starting from the 3-months lag, the 1-month NI will be tested only if the 3-months NI will be demonstrated.

The following modification of the primary objective will be applicable if the per-protocol set is not reached for the Sh_NTHi-Mcat_6 and the Sh_NTHi-Mcat_3 groups:	
Considering the sampling timepoint at 1 month after Dose 2 of NTHi-Mcat vaccine, the 2-sided 95% CIs for the group GMC ratio (Sh_NTHi-Mcat_1 group over NTHi-Mcat group) of anti-PD, anti-PE, anti-PiA, anti-UspA2 will be computed using an analysis of covariance (ANCOVA) model on the logarithm10 transformation of the concentrations. The ANCOVA model will include study group, smoking status (current or former), age category (50–59, 60–69, 70–80 years of age) and centre as factors and the antibody concentration before Dose 1 as covariate.
 
Non-inferiority for a specific time-lag will be claimed if the lower limit of the 2-sided 95% CI for the GMC ratio will be above 0.667 for all anti-PD, anti-PE, anti-PiA, anti-UspA2.

Secondary endpoints	
Secondary - humoral	
Within group assessment
 
For each study group, for each sampling timepoint and for each antigen, the following statistics will be computed:
 
 
• Seropositivity rates with exact 95% CI (seropositivity defined using the assay lower limits of quantification [LLOQ])
 
• Adjusted and unadjusted GMCs with 95% CI (adjustment by ANCOVA model, as specified above)
 
• The range and distribution of antibody concentrations
 
 
The distribution of antibody concentrations for each antigen will be displayed using reverse cumulative distribution curves.

Secondary –cell-mediated immune response	
CMI response induced by the NTHi-Mcat candidate vaccine will be evaluated, presenting the frequencies of antigen-specific CD4+ T cells per <math>10^6</math> cells. The specific CD4+ T cells being identified as the CD4 + T cells expressing at least 2 different markers among CD40 Ligand (CD40L), IL-2, TNF- <math>\alpha</math>, IFN- <math>\gamma</math>, IL-13 and IL-17 upon in vitro stimulation.
 
Descriptive statistics (Min, Q1, Median, Mean, Q3 & Max) will be reported for each group at pre-Dose 1 of the NTHi-Mcat investigational vaccine (Day 91; Day 151; Day 241 in the Sh-NTHi-Mcat groups and Day 1 in the NTHi-Mcat group), and 1 month after Dose 2 of NTHi-Mcat investigational vaccine (Day 181; Day 241; Day 331 in the Sh_NTHi-Mcat groups and Day 91 in the NTHi-Mcat group).

**CONFIDENTIAL**

209538 (NTHI MCAT-009)  
 Statistical Analysis Plan Amendment 2

Endpoint	Statistical analysis methods
Tertiary –cell-mediated immune response	
 
• CMI response induced by the NTHi-Mcat candidate vaccine will be evaluated, presenting the frequencies of antigen-specific CD8+T cells per <math>10^6</math> cells. The specific CD8+T cells being identified as the CD8+ T cells expressing at least 2 different markers among CD40L, IL-2, TNF- <math>\alpha</math>, IFN- <math>\gamma</math>, IL-13 and IL-17 upon in vitro stimulation.
 
• CMI response as the frequencies of specific CD4+/CD8+ T cells per <math>10^6</math> cells expressing any combination of cytokines/activation markers will be determined. The T-helper profile of the specific T-cell response in T-helper 1, T-helper 2 and T-helper 17 based on the specific expression of respectively IFN-<math>\gamma</math>, IL-13 and IL-17 will be characterized.
 
 
Descriptive statistics (Min, Q1, Median, Mean, Q3 & Max) will be reported for each group at pre-Dose 1 of the NTHi-Mcat investigational vaccine (Day 91; Day 151; Day 241 in the Sh-NTHi-Mcat groups and Day 1 in the NTHi-Mcat group), and 1 month after Dose 2 of NTHi-Mcat investigational vaccine (Day 181; Day 241; Day 331 in the Sh_NTHi-Mcat groups and Day 91 in the NTHi-Mcat group).

 A descriptive analysis where the 95% confidence intervals around the geometric mean concentration (GMC) ratio of the Sh\_NTHi-Mcat\_6 group will be presented with all available data. The descriptive analysis may be used to support the interval between Shingrix and NTHi-Mcat vaccines administration

 A descriptive analysis where the 95% confidence intervals around the geometric mean concentration (GMC) ratio of the Sh\_NTHi-Mcat\_6 and Sh\_NTHi-Mcat\_3 groups will be presented with all available data. The descriptive analysis may be used to support the interval between Shingrix and NTHi-Mcat vaccines administration

### **5.3.2. Additional considerations**

The supplementary analysis based on the mFAS will be performed if the percentage of mFAS subjects excluded from the PPS is more than 10%.

#### **5.3.2.1. Analysis of humoral response**

##### **Hypothesis related to the primary objective**

The global null hypothesis related to the primary objective of the study is that at least 1 GMC ratio (Sh\_NTHi-Mcat over NTHi-Mcat) among anti-PD, anti-PE, anti-PilA, anti-UspA2 is inferior or equal to 0.667 in all time-lags under investigation at 1 month post-Dose 2 of NTHi-Mcat vaccine. This must be rejected in favour of the alternative hypothesis that all 4 GMCs (anti-PD, anti-PE, anti-PilA, anti-UspA2) are non-inferior in at least one time-lag group. Family-wise type I error is fixed at 2.5% (1-sided).

##### **Geometric mean concentration and geometric mean concentration ratio**

For each antigen and study group, at 1 month after Dose 2 of NTHi-Mcat vaccine, adjusted GMCs and GMCs ratios with corresponding 95% CIs will be obtained exponentiating (base 10) the least square means and the lower and upper limits of the 95% CIs derived from the ANCOVA model. The ANCOVA model will be implemented in SAS, similarly to the following code:

```
PROC GLM data=<dataset>;
BY antigen;
class group age smoking_status centre;
MODEL log(concentr)= group age smoking_status centre log(pre_concentr);
LSMEAN group / CL PDIFF ALPHA=0.05;
RUN;
```

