**10.1.3.4. Geometric mean concentrations (GMCs)**

GMC calculations are performed by taking the inverse logarithm of the mean of the log-10 concentration transformations. Antibody concentrations below the cut-off of the assay will be given an arbitrary value of half the cut-off of the assay for the purpose of GMC calculation. The cut-off value is defined by the laboratory before the analysis and is described in the protocol.

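### The illustrative SAS code for the primary ANCOVA uses log() where the SAP text requires log10: a template error to correct, with the planned method and the 0.667 margin unchanged

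*SAP*

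**What the plan says.** SAP 5.3.1 sets the scale of the primary analysis: the confidence intervals for the GMC ratios come from an "analysis of covariance (ANCOVA) model on the logarithm10 transformation of the concentrations". The decision rule in the same table is "Non-inferiority for a specific time-lag will be claimed if the lower limit of the 2-sided 95% CI for the GMC ratio will be above 0.667", and each of the four antigens must meet it.

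SAP 5.3.2.1 then says how the estimates are produced. Adjusted GMCs and ratios "will be obtained exponentiating (base 10) the least square means and the lower and upper limits of the 95% CIs". The code follows, introduced by "The ANCOVA model will be implemented in SAS, similarly to the following code", and its model line is "MODEL log(concentr)= group age smoking_status centre log(pre_concentr". No base is written in the code.

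Two other places use base 10. The permutation test in SAP 5.3.2.1 shifts the data by 0.176, given as -log10(0.667), although it calls the data only logarithmically transformed. SAP 10.1.3.4 says "GMC calculations are performed by taking the inverse logarithm of the mean of the log-10 concentration transformations".

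The same model line stands in all three SAP versions in the file, including the current Amendment 2.

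**The concern.** The code and the sentence that introduces it use different bases if log() is read as SAS reads it. Taking natural logs and then raising 10 to the result does not return the original quantity. Every GMC, ratio and confidence limit produced in that way would be on the wrong scale, and the fixed threshold of 0.667 would be applied to distorted limits.

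This is the specification of the confirmatory analysis, so a mismatch here deserves more attention than one in background text. The time-lags are tested in sequence, so a false failure at the first lag would also block the later ones. The permutation test might not act as a check. It refits the ANCOVA and adds a base-10 shift to data whose base is not stated, so the same slip could enter there too.

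**Working it through.** **Inputs.** Margin 0.667 (SAP 5.3.1). SD 0.36 on the log10 scale, true difference 0, 108 evaluable subjects per group, target power 94.6% per antigen and 80% for four antigens assuming independence (protocol 10.1.2). One-sided alpha 2.5% (SAP 5.3.2.1). That log() means the natural logarithm is a convention of the software; the documents do not state it.

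**1. The plan's own figures, on log10.**
- Margin: -log10(0.667) = 0.1759, matching the 0.176 in the permutation test.
- Standard error: 0.36 × √(2/108) = 0.0490.
- Non-central t power at 108 per group: 94.7% per antigen; 0.9467^4 = 80.3% for four.
- Inflation for 20% loss: 108/0.80 = 135.

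The design reproduces on log10, which confirms the intended scale.

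**2. Natural log carried into a base-10 back-transformation.**
- Reported ratio = 10^(ln r) = r^(ln 10) = r^2.3026.
- The reported limit exceeds 0.667 only if r > 0.667^(1/2.3026) = exp(-0.1759) = 0.8387.

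| Correct value | Would be reported as |
|---|---|
| 0.70 | 0.44 |
| 0.80 | 0.60 |
| 0.90 | 0.78 |
| 1.00 | 1.00 |
| 1.10 | 1.25 |
| GMC of 1000 EU/mL | about 8.1 million |

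**3. Where the planned design sits.** With an observed ratio of 1, the half-width is 1.96 × 0.0490 = 0.0960 on log10, so the correct lower limit is 10^(-0.0960) = 0.80. Non-inferiority is met. The reported limit would be about 0.60, a failure. The affected band (0.667 to 0.839) therefore includes the limit expected under the design assumptions.

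**4. Power under that hypothetical slip.** The margin of 0.8387 is 0.0764 on log10. With SE 0.0490, power is about 34% per antigen and 0.3417^4 = 1.4% for four, assuming independence. These figures describe a faulty program, not the plan.

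**5. Permutation test.** Adding 0.176 to natural-log data would test exp(-0.176) = 0.839, the same displaced margin.

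**6. Direction.** 0.839 is above 0.667, so the slip makes the criterion stricter. It can miss non-inferiority but cannot create a false claim.

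**7. The covariate.** Changing the log base of the baseline value rescales its coefficient and leaves the group contrasts unchanged. Only the base of the response matters for the result.

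**The case against.** The strongest reply is that the code is illustrative and the text governs. It is introduced as similar to what will be run, it has a placeholder for the dataset, and the SAP itself departs from it: the contrasts are listed separately, and SAP 10.1.5.3 asks for two-level covariates as dummy continuous variables, whereas the code puts smoking status in the CLASS statement. A programmer will in practice derive the transformed variables first, and the text for that step says log10. Unadjusted GMCs are also to be presented, computed on log10 under SAP 10.1.3.4, so an adjusted GMC in the millions beside them would be hard to miss.

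Nearly all of this stands. It rules out two inferences that a reader might draw: that the SAP has moved the margin to 0.839, and that the trial's power is really 1.4%. The text fixes log10 and 0.667 throughout, so neither follows. Nor is the code the only usable specification of the analysis.

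The reply does not remove the contradiction. Wording that allows similar code covers differences in syntax; it does not settle which base applies to the primary endpoint. Distorted ratios near 1 are also much less conspicuous than distorted GMCs.

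**Conclusion.** The code template contradicts the stated scale of the primary analysis and should be corrected. The planned analysis is sound: log10 response, base-10 back-transformation, margin 0.667.

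The harm is conditional. It requires that log() be taken as the natural logarithm, that this be carried through to the base-10 back-transformation, and that nobody notice. Ratios would then be reported as r^2.303, and non-inferiority would be missed for correctly computed lower limits between 0.667 and about 0.839. Decisions outside that band would not change, and type I error would not rise. Because the outputs would probably look implausible, this is an inexpensive safeguard for the confirmatory decision and not evidence of a wrong result.

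**What to change.** In the SAP 5.3.2.1 code, replace the two log() terms with derived log10 variables, for example `MODEL log10_post = group age smoking_status centre log10_pre`. The response is the essential change; the covariate is changed for consistency. In the permutation test, state that the logarithmic transformation is log10. Leave the base-10 back-transformation, the 0.176 shift, the 0.667 margin and the sample size as they are.

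The cost is one line of code and one clarifying term in the SAP. Study conduct and data collection are not affected.

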**CONFIDENTIAL**

209538 (NTHI MCAT-009)  
 Statistical Analysis Plan Amendment 2

Contrasts to be included: Sh\_NTHi-Mcat\_6 vs NTHi-Mcat, Sh\_NTHi-Mcat\_3 vs NTHi-Mcat, Sh\_NTHi-Mcat\_1 vs NTHi-Mcat.

In addition, unadjusted GMCs and GMRs will be presented for each timepoint (pre-Dose 1 and post-Dose 2 of NTHi-Mcat vaccine) with a descriptive purpose.

**Permutation test (sensitivity analysis on primary objectives)**

Based on the covariate-adaptive treatment assignment algorithm (see Section 10.3), the following permutation test will be performed as a sensitivity analysis on the primary objectives [Wiens, 2006, Hasegawa, 2009 and Ernst, 2004] in the PPS.

For each antigen, let  $\mathbf{X}=(X_1, \dots, X_N)$  the logarithmically-transformed antibody concentrations for the NTHi-Mcat group and  $\mathbf{Y}_{1/3/6}=(Y_1, \dots, Y_N)$  the logarithmically-transformed antibody concentrations for one of the Sh\_NTHi-Mcat groups at 1 month after Dose 2 of NTHi-Mcat vaccine, a non-inferiority permutation test can be obtained from a superiority permutation test on  $\dot{\mathbf{X}}=(X_1, \dots, X_N)$  against  $\dot{\mathbf{Y}}_{1/3/6}=(Y_1 + \delta, \dots, Y_N + \delta)$  with  $\delta = 0.176 = -\log_{10}(0.667)$ .

The original treatment assignment algorithm will be used to re-randomize subjects while keeping antibody concentrations, covariates and entry order as observed. The procedure will be as follows:

1. Fit the ANCOVA model to obtain the test statistics  $T^*_{1/3/6}$  for the superiority of  $\dot{\mathbf{X}}$  against  $\dot{\mathbf{Y}}_{1/3/6}$ .
2. Estimate the distribution of the test statistics with  $R=10000$  repetitions of the following 2 steps:
  - a. Re-randomize treatment assignment of all 4 groups (original algorithm).
  - b. Re-fit the ANCOVA model to re-obtain the test statistics  $T_{1/3/6}$ .
3. Derive the permutation p-values associated to the observed test statistics (from step 1) based on the empirical distributions in Step 2

$$p_{1/3/6} = M+1/R+1$$

Where  $M$  is the number of repetitions such that  $T_{1/3/6} \geq T^*_{1/3/6}$ .

 if the primary objective, following the assessment in term of number of subjects in PPS, is based on a reduce number of groups, the permutation p-values associated to the observed test statistics will be derived only for the groups participating to the primary objective.

**CONFIDENTIAL**209538 (NTHI MCAT-009)  
Statistical Analysis Plan Amendment 2**Seropositivity rate and fold increase**

For each antigen, timepoint and study group, the seropositivity rate (defined as the proportion of subjects with an antibody concentration greater or equal to the assay cut-off) with exact 95% CIs will be computed using the method referenced in section 10.1.5.1. Assay cut-offs are reported in section 9.1.1. In addition, percentages of subjects with a 2/4/8-fold increase will be presented with associated 95% CI.

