**LIST OF FIGURES**

	PAGE
Figure 1      Study design overview .....	9
Figure 2      Sequence for evaluating the primary objective in order to control the overall type I error below 2.5% (one-sided) in case all groups reached the number of subjects planned in the PPS .....	26

**CONFIDENTIAL**209538 (NTHI MCAT-009)  
Statistical Analysis Plan Amendment 2**LIST OF ABBREVIATIONS**

AE	Adverse event
ANCOVA	Analysis of Covariance
ANOVA	Analysis of Variance
CI	Confidence Interval
CMI	Cell-Mediated Immune
COVID-19	Coronavirus Disease 2019
CSR	Clinical Study Report
CTRS	Clinical Trial Registry Summary
eCRF	Electronic Case Report Form
ELISA	Enzyme-linked immunosorbent assay
ES	Exposed Set
eTMF	Electronic Trial Master File
EU/mL	ELISA unit per milliliter
FAS	Full Analysis Set
GMC	Geometric mean antibody concentration
GMR	Geometric mean ratio
GSK	GlaxoSmithKline
LL	Lower Limit
LLOQ	Lower Limit of Quantification
MedDRA	Medical Dictionary for Regulatory Activities
mFAS	Modified Full Analysis Set
NA	Not Applicable
NI	Non-Inferiority
PD	Protocol Deviation

**CONFIDENTIAL**209538 (NTHI MCAT-009)  
Statistical Analysis Plan Amendment 2

PPS	Per-Protocol Set
RCD	Reverse cumulative distribution
SAE	Serious adverse event
SAP	Statistical Analysis Plan
SBIR	GSK Biological's Internet Randomization System
SD	Standard Deviation
SDTM	Study Data Tabulation Model
SR	Study Report
TFL	Tables Figures and Listings
ToC	Table of Content

**CONFIDENTIAL**209538 (NTHI MCAT-009)  
Statistical Analysis Plan Amendment 2**1. DOCUMENT HISTORY**

[figure not shown]
Date	Description	Protocol Version
01 APR 2019	First version	Protocol Administrative Change 1: 14 DEC 2018
30 JAN 2020	Amendment 1: 
 
Section 5.3.2.1: update to the permutation test algorithm (recommendation from Center for Biologics Evaluation and Research)
 
	Protocol Administrative Change 1: 14 DEC 2018
20 MAY 2020	Amendment 2: 
 
Section 3: Objectives and endpoints
 
Section 4.2.4.1: Elimination codes from Per Protocol Set
 
Section 5.3.1: Analysis of immunogenicity planned per protocol
 
Section 5.3.2.1: Analysis of humoral response
 
Section 6: Analysis interpretation
 
	Protocol Amendment 1: 18 MAY 2020

CONFIDENTIAL

209538 (NTHi MCAT-009)  
Statistical Analysis Plan Amendment 2

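### The SAP's permutation test for non-inferiority is specified in the wrong direction: followed literally, its p-value is about 1 minus the correct one

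*SAP*

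**What the plan says.** The primary criterion (SAP section 3 and section 5.3.1; Protocol section 10.3.4) is that the lower 95% confidence limit of the GMC ratio, Shingrix-first group over control, exceeds 0.667 for all four antigens. Below, the three groups given Shingrix before NTHi-Mcat are called the Sh groups.

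The permutation test in SAP section 5.3.2.1 is a sensitivity analysis of that result. It takes X to be "the logarithmically-transformed antibody concentrations for the NTHi-Mcat group" and Y to be the "antibody concentrations for one of the" Sh groups. It adds delta = 0.176, which is minus log10 of 0.667, to every Y and leaves X alone. It then states that "a non-inferiority permutation test can be obtained from a superiority permutation test on" X against the shifted Y.

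Step 1 fits the ANCOVA to obtain T* "for the superiority of $\dot{\mathbf{X}}$ against $\dot{\mathbf{Y}}_{1/3/6"; in this notation the dotted X is the unshifted control and the dotted Y is the Sh group plus delta. Step 2 re-randomises all four groups R = 10000 times with the minimisation algorithm of section 10.3. Step 3 lets M count the repetitions with T at or above T* and forms the p-value from M+1 and R+1. No formula for T is given.

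Just above, the same section lists the ANCOVA comparisons in the other order: "Contrasts to be included: Sh\_NTHi-Mcat\_6 vs NTHi-Mcat", and likewise for the 3-month and 1-month groups.

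**The concern.** Adding delta to the Sh group turns non-inferiority into a superiority question: does Y + delta exceed X? Step 1 asks the reverse, whether the control exceeds the shifted Sh group, and step 3 then takes the upper tail of that statistic. A small p under those instructions is evidence that the Sh group lies below the margin, which is inferiority.

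This is the only planned analysis whose reference distribution comes from the actual minimisation algorithm. Run as written, it would look unsupportive when non-inferiority is clear and would return small p-values when the Sh group is clearly worse. Because the contrasts and step 1 point in opposite directions and nothing settles the sign, two programmers working independently from this text could report p near 0 and p near 1 from the same data. Settling the sign after results are known, in an open-label trial, would be a post hoc choice.

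**Working it through.** **Inputs.** Margin 0.667, SD 0.36 on the log10 scale, true difference 0, 108 evaluable per group, one-sided 2.5% (Protocol section 10.1.2; SAP section 5.3.2.1).

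**Reproducing the plan's own figures.**
- delta = -log10(0.667) = 0.17587, which rounds to the stated 0.176.
- Standard error = 0.36 x sqrt(2/108) = 0.04899.
- Expected z at a true ratio of 1 = 0.17587/0.04899 = 3.59.
- Power per antigen with the noncentral t at n = 108 is 94.67%; to the fourth power this is 80.3%. The smallest n reaching 80% for all four antigens is 108. The protocol states 94.6% and 80%.
- 108/0.8 = 135 randomised per group, as stated.

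**Direction.** Ratio above 0.667 means mean(Y) - mean(X) > -delta, that is, mean(Y + delta) > mean(X). Let S = [adjusted mean(Y + delta) - adjusted mean(X)]/SE. The correct p counts S at or above S*. The literal statistic is T = -S, so its upper tail counts S at or below S*. The two counts add to R plus ties, so

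p(literal) + p(correct) = (R + ties + 2)/(R + 1) = 1 + (1 + ties)/(R + 1).

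This holds whatever the number of centres or the covariate distribution.

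**Size, normal approximation.** With z = (log10(ratio) + 0.17587)/0.04899, the chance of p <= 0.025 is Phi(z - 1.96) in the correct direction and Phi(-z - 1.96) as written:

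| True ratio | z | Correct | Literal |
|---|---|---|---|
| 1.0 | 3.59 | 94.8% | about 1e-8 |
| 0.8 | 1.61 | 36.4% | 0.02% |
| 0.667 | 0 | 2.5% | 2.5% |
| 0.6 | -0.94 | 0.19% | 15.3% |
| 0.5 | -2.55 | 0.0003% | 72.4% |

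At z = 3.59 the correct p is 0.00017 and the literal p is 0.99983. The 94.8% agrees with the planned response-wise power of 94.6%, which confirms which direction was intended.

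**Re-randomisation with the section 10.3 algorithm.** 432 subjects, three factors with equal weight, 90% deterministic, four-group ANCOVA, delta added to all Sh groups.

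- *One simulated trial, R = 1000, 15 centres (assumed), the same random draws at each ratio.* Three p-values, one per Sh group. Ratio 1: correct 0.001 each, literal 1.000 each. Ratio 0.8: correct 0.075, 0.072, 0.024; literal 0.926, 0.929, 0.977. Ratio 0.5: correct 0.997, 0.996, 0.986; literal 0.004, 0.005, 0.015. Every pair summed to 1.001 = 1 + 1/1001 to the precision shown.
- *200 trials x 3 groups = 600 comparisons per setting, R = 2000.* The number of centres (10 or 20) and the pre/post correlation (0 or 0.4) are assumptions; ranges run over them.
  - Ratio 1: median literal p 1.000, median correct p 0.0005. Agreement with the confidence-interval decision at 0.025 was 2.7% to 5.5% literal and 98.8% to 100% correct.
  - Ratio 0.5: literal p <= 0.025 in 72% to 81%, correct p <= 0.025 in 0%.
  - At the margin: correct p <= 0.025 in 2.3% to 2.5%, as it should be.
  - Wherever the confidence interval showed non-inferiority, in any setting, the literal p was never below 0.966. The few literal agreements at ratio 1 are therefore comparisons where the interval itself failed.

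**The case against.** The strongest reply is that the surrounding text shows what was meant. The procedure is labelled a non-inferiority test, delta is added to the correct arm, and the contrasts are listed as Sh versus control. A programmer who takes that contrast as T and keeps the upper tail gets the right p. This stands: the error is in the written specification and need not be in the code. It does not rescue the wording, because superiority of X over shifted Y with an upper tail has no reading that tests non-inferiority of the Sh group.

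It can also be said that the practical risk is small. The primary decision rests on the confidence limit, the primary ANCOVA already adjusts for all three minimisation factors, and a p near 1 beside an interval clearly above 0.667 would be noticed. All true, and this limits the importance of the point. At intermediate effects the error is less obvious: at a true ratio of 0.8 the literal p ran from 0.40-0.47 (2.5th percentile) up to 1.00, which could pass for a merely inconclusive result.

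The SAP names no cut-off for this p-value. It says "Family-wise type I error is fixed at 2.5% (1-sided" for the primary hypothesis, and a sensitivity analysis does not strictly need a pass/fail rule, so that omission is minor. The document history records an "update to the permutation test algorithm (recommendation from Center for Biologics Evaluation and Research"). Comparing the versions, what changed was the re-randomisation, from pairwise to all four groups; the content of the recommendation is not given, so nothing can be inferred from it about direction.

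**Conclusion.** The point holds. Step 1 of the permutation test names the wrong arm as superior, so the literal p-value is 1 minus the correct one, up to 1/(R+1) and ties. Under the planning assumptions (SD 0.36, 108 per group, ratio 1) that is about 0.9998 in place of about 0.0002. At a true ratio of 0.5 the literal test would reach 0.025 about 72% of the time by normal approximation, and 72% to 81% by simulation. The complement relation needs no assumptions beyond few ties; the simulated percentages depend on the assumed centres, covariates and pre/post correlation.

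The same step 1 wording stands in the April 2019 SAP, Amendment 1 and Amendment 2, so it is not a text-extraction fault. The effect is confined to the sensitivity analysis; the primary non-inferiority decision is not touched.

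**What to change.** In SAP section 5.3.2.1, step 1, define T* for the superiority of the shifted Sh group over the control, with the formula T* = [LS mean(Y + delta) - LS mean(X)]/SE on the log10 scale. Leave the upper tail in step 3 as it is, and say that p is read against one-sided 0.025.

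Two editorial corrections belong in the same edit. Write p = (M+1)/(R+1) with brackets, since the printed form without them exceeds 1. Use log10 in the illustrative SAS code, to match the log10 model text and the base-10 back-transformation.

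The cost is one line of wording, a stated level and the two corrections. Data, design and primary analysis do not change. If the program already exists, its sign should be checked against the new formula.
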